4.4.1 Inclusion Criteria

Subjects must meet the following inclusion criteria to participate in the study.

1. Consenting adult aged 18 – 75 years at screening.
2. Have a diagnosis of plaque-type psoriasis for ≥ 6 months prior to screening.
3. Must have chronic plaque-type psoriasis of moderate severity confirmed at both Screening and Baseline visits. Moderate severity is defined as:
 - PASI > 7 with BSA involvement of 5 – 15% inclusive, and
 - overall lesion severity of moderate or marked, where:
 - moderate = moderate plaque elevation (= 0.75mm); moderate red coloration; coarse scale predominates;
 - marked = moderate plaque elevation (= 1mm); bright red coloration; thick, non-tenacious scale predominates.
4. Female subjects of childbearing potential must use two highly effective forms of contraception, unless surgically sterilized, partner has had a vasectomy, or they will be abstinent during study participation and for 30 days after their last dose of study drug. Highly effective methods of birth control in this study include intrauterine device, hormonal contraception (oral, patch, injectable, implant) or double-barrier method (condom or diaphragm with spermicide). This contraception must be continued during the study and for 30 days after taking the last dose of study drug. (Post-menopausal defined as lack of menses for ≥ 6 months prior to screening confirmed with serum follicle stimulating hormone (FSH) > 25 mIU/mL at screening.)
5. Male subjects with partners of childbearing potential must take appropriate precautions to avoid fathering a child while participating in the study and use appropriate barrier contraception or abstinence during the study and for 30 days after their last dose of study drug.

LYC-30937

Clinical Protocol LYC-30937-2003

Issue Date: 30 August 2016

6. Agree to avoid prolonged sun exposure and avoid tanning booths or UV light sources during the study.
7. Ability to provide written informed consent and to be compliant with the schedule of events.

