8.5.2 Secondary Efficacy Endpoint Analyses

The following secondary efficacy endpoints will be summarized and compared between the LYC-30937-EC treatment arm and placebo:

- The proportion of subjects who achieve a $\geq 75\%$ reduction from baseline in PASI at Week 12 will be calculated by taking the number of subjects who achieve a $\geq 75\%$ reduction from baseline in PASI at Week 12 divided by the total number of subjects in each treatment arm. The proportion of subjects in each treatment arm will be compared using a chi-square test.
- The mean percent change from baseline to Week 12 in the BSA will be calculated by taking the Week 12 BSA and subtracting the baseline percent BSA then dividing by the baseline percent BSA and multiplying by 100 to get the percentage of baseline. The mean percent change in each treatment arm will be compared using the same methodology for the primary efficacy endpoint.
- The proportion of subjects who achieve “cleared” (score = 0) or “minimal” (score = 1) on the static IGA at Week 12 will be calculated by taking the number of subjects who achieve “cleared” (score = 0) or “minimal” (score = 1) on the static IGA at Week 12 divided by the total number of subjects in each treatment arm. The proportion of subjects in each treatment arm will be compared using a chi-square test.
- The proportion of subjects who achieve at least a 2 step reduction on the static IGA at Week 12 will be calculated by taking the number of subjects who achieve at least a 2 step reduction on the static IGA at Week 12 (ie, a score of 5 at baseline to a score of 3 or less at Week 12) divided by the total number of subjects in each treatment arm. The proportion of subjects in each treatment are will be compared between treatment arms using a chi-square test.

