3.5 Study Endpoints

3.6 Efficacy Endpoint

The primary efficacy endpoint of the study will be the mean percent change from baseline at Week 12 in PASI.

The secondary efficacy endpoints of the study will be:

- The proportion of subjects who achieve a $\geq 75\%$ reduction from baseline in PASI at Week 12.
- The mean percent change from baseline to Week 12 in the %BSA.
- The proportion of subjects who achieve “cleared” (score = 0) or “minimal” (score = 1) on the static IGA at Week 12.
- The proportion of subjects who achieve a 2 step reduction on the static IGA at Week 12.

The exploratory efficacy endpoints of the study will be:

- The proportion of subjects who achieve a $\geq 50\%$ reduction from baseline in PASI at Week 12.
- The proportion of subjects who achieve a $\geq 25\%$ reduction from baseline in PASI at Week 12.
- Proportion of subjects achieving both a $\geq 75\%$ reduction from baseline in PASI and a static IGA score of 0 (cleared) or 1 (minimal) at Week 12.

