- The proportion of subjects who achieve “cleared” (score = 0) or “minimal” (score = 1) on the static IGA at Week 12 will be calculated by taking the number of subjects who achieve “cleared” (score = 0) or “minimal” (score = 1) on the static IGA at Week 12 divided by the total number of subjects in each treatment group.

The proportion of subjects in each treatment group will be compared using chi-square test. The difference in proportion of subjects who achieve “cleared” (score = 0) or “minimal” (score = 1) on the static IGA at Week 12 (LYC-30937-EC versus placebo) will also be estimated along with the 95% confidence interval. If the confidence interval does not contain 0 the null hypothesis will be rejected and the proportion of subjects who achieve “cleared” (score = 0) or “minimal” (score = 1) on the static IGA at Week 12 will be considered different due to treatment arm.

- The proportion of subjects who achieve at least a 2 step reduction on the static IGA at Week 12 will be calculated by taking the number of subjects who achieve at least a 2 step reduction on the static IGA at Week 12 (i.e., a score of 5 at baseline to a score of 3 or less at Week 12) divided by the total number of subjects in each treatment group. The results will be summarized and analyzed using the same methodology as for the proportion of subjects who achieve “cleared” (score = 0) or “minimal” (score = 1) on the static IGA at Week 12.

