6.10.2 Demographics and Baseline Characteristics

Demographic information and subject characteristics such as sex, race, age, smoking status, drug and alcohol consumption, menopausal status, duration of chronic plaque-type psoriasis, will be summarized for FAS by treatment group and overall and listed by subject.

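### The 2-step static IGA endpoint sets its threshold by baseline score (3 or 4), but the planned chi-square ignores baseline and the only worked case starts from a score that entry does not admit

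*SAP*

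**What the plan says.** **The rule and its example.** SAP 6.2 defines the endpoint as "at least a 2 step reduction on the static IGA at Week 12" and explains it by "i.e., a score of 5 at baseline to a score of 3 or less at Week 12". Protocol 8.5.2 gives the same single case: "ie, a score of 5 at baseline to a score of 3 or less at Week 12". The endpoint lists (Protocol 1.0 and 3.2, SAP 3.6) leave out the words that make it a minimum: "The proportion of subjects who achieve a 2 step reduction on the static IGA at Week 12".

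**Who can enter.** Protocol 4.4.1, criterion 3: "Must have chronic plaque-type psoriasis of moderate severity confirmed at both Screening and Baseline visits". It requires "overall lesion severity of moderate or marked, where" the lower level is "moderate = moderate plaque elevation (= 0.75mm); moderate red coloration; coarse scale predominates". That is the descriptor of static IGA 3 in Protocol 6.3.2, and the descriptor for marked is that of IGA 4. The IGA 5 descriptor does not appear in the criterion.

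**The analysis.** SAP 6.2 handles this endpoint like IGA 0/1: a chi-square test, and a difference in proportions with a 95% interval. No baseline term is planned, and Protocol 5.3 names no stratification factor. Continuous efficacy endpoints, by contrast, are adjusted for baseline (SAP 5.1). SAP 5.1 calls the secondary p-values descriptive.

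**The baseline tables.** Protocol 8.3 asks for baseline static IGA by arm. SAP 6.10.2 names "sex, race, age, smoking status, drug and alcohol consumption, menopausal status, duration of chronic plaque-type psoriasis" and not static IGA. SAP 6.2 plans no by-visit IGA summary, and SAP 7 does not record the omission as a change.

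**The concern.** The documents' only worked case cannot arise in a correctly enrolled subject, and it shows a finish at 3, which is itself an entry-level severity. The cases that can arise, starts at 3 and at 4, are not spelled out, and they face different thresholds. A subject starting at 4 may count as a responder with mild disease; one starting at 3 may not.

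The arm rates therefore depend on how many subjects in each arm start at 4, unless response is equally likely from both starting scores. In a trial of 30 without stated stratification, that mix can differ noticeably by chance. At stake is the precision and reading of one secondary endpoint, and a reader's ability to see from the named tables whether the mix was balanced.

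**Working it through.** **1. The plan's own figure.** The only design figure is for the primary endpoint (SAP 5.2: 20 versus 10, difference 36.0, SD 32.0, two-sided t-test, alpha 0.05). The noncentrality is 36 / (32 × √(1/20 + 1/10)) = 2.90 on 28 df, giving power 0.8006. The stated 80% reproduces. No rate or power is given for the 2-step endpoint.

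**2. Which Week 12 scores count.** A drop of at least 2 gives:

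| Baseline IGA | 2-step responders | IGA 0/1 responders | Admitted by criterion 3 |
|---|---|---|---|
| 3 | 0, 1 | 0, 1 | yes |
| 4 | 0, 1, 2 | 0, 1 | yes |
| 5 | 0, 1, 2, 3 | 0, 1 | no |

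Among eligible subjects, every IGA 0/1 responder is a 2-step responder, and the only additions are subjects who go from 4 to 2.

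**3. Chance imbalance.** Treat the numbers starting at IGA 4 as independent Binomial(20, q) and Binomial(10, q). The true share q is not in the documents, so a range is shown.

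| q | P(shares differ by ≥ 20 points) | P(≥ 30 points) |
|---|---|---|
| 20% | 26% | 7% |
| 30% | 33% | 12% |
| 50% | 37% | 16% |

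These are two-sided; about half of each figure lies in either direction.

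**4. Effect on the arm difference with no drug effect.** Let a and b be the response rates from baseline 3 and 4, and m the arm's share at IGA 4. The arm rate is (1 − m)a + mb, so the expected gap is (m_active − m_placebo)(b − a). Both a and b are assumptions.

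| a, b | shares 20% vs 40% | shares 30% vs 60% |
|---|---|---|
| 5%, 10% | −1 point | −1.5 points |
| 5%, 20% | −3 points | −4.5 points |
| 10%, 40% | −6 points | −9 points |

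If a = b the gap is zero. For comparison, at 16% versus 22% (the −6 case) the standard error of the difference is √(0.16 × 0.84/20 + 0.22 × 0.78/10) = 0.155, about 15 points.

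**5. Share of the noise due to the mix.** With p = (1 − q)a + qb, the fraction of the null variance of the arm difference that comes from the mix is q(1 − q)(b − a)² / [p(1 − p)].
- a = 10%, b = 40%, q = 30%: p = 0.19, so 0.21 × 0.09 / 0.1539 = 12%. Removing it would cut the standard error by 1 − √0.88, about 6%.
- a = 5%, b = 20%, q = 30%: p = 0.095, so 0.21 × 0.0225 / 0.0860 = 5.5%, a cut of about 3%.
- a = 5%, b = 10%, q = 20%: p = 0.06, so 0.16 × 0.0025 / 0.0564 = 0.7%, a negligible cut.

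**6. Type I error of the unadjusted chi-square (exact binomial).** Settings (a, b, q): (5%, 20%, 30%), (10%, 30%, 50%), (10%, 40%, 50%). Averaged over random mixes, the null rejection rate is 3.7% to 4.3%. Given particular numbers at IGA 4, it is:
- 4/20 versus 5/10: 6.2% to 7.5%
- 14/20 versus 3/10: 1.8% to 6.3%
- 10/20 versus 5/10 (balanced): 3.1%

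**7. What stratifying buys.** I simulated 200,000 trials per setting for the three settings in step 6 and (10%, 40%, 30%), with drug effects of 0, 30 or 40 points added in both strata. The Cochran-Mantel-Haenszel test rejected in 3.4% to 4.5% of null trials. Its power differed from the chi-square's by −0.3 to +1.8 points. The Mantel-Haenszel risk difference had a standard error between 0.4% larger and 5.5% smaller than the crude difference. Other assumed rates gave power gains of about 1 to 5 points and a standard error up to about 10% smaller.

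**The case against.** The strongest reply is that this is a slip of wording plus ordinary chance imbalance. Several parts of that reply stand.

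- **A reader might infer that the endpoint is undefined, or that no eligible subject can respond.** The documents do not support that. The minimum two-step drop is complete and can be programmed; the 5-to-3 case is most likely an example introduced by the wrong abbreviation. The bar on IGA 5 is itself an inference from matching descriptors, since criterion 3 speaks of lesion severity and not of the static IGA. A subject enrolled in error at 5 would stay in the full analysis set.
- **A reader might infer bias or a raised false-positive rate.** Randomization keeps the comparison unbiased on average, and overall rejection stays below 5% in every setting tried. The conditional excess at 4/20 versus 5/10 is small.
- **A reader might take the overlap with IGA 0/1 as an error.** Nested response thresholds are common, and SAP 3.6 uses them for PASI too. The overlap only needs to be stated.
- **A reader might think all baseline severity tables were dropped.** SAP 6.1 and 6.2 already summarize baseline PASI and %BSA by arm. Only static IGA is unnamed. The SAP 6.10.2 list is introduced as examples, and Protocol 8.3 still requires the summary.
- **Strata would be small.** At a 30% share, about 6 versus 3 subjects would start at IGA 4, so the gain is limited.

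What does not stand is leaving the analysis as it is. The variable that sets the threshold is already collected, and the plan adjusts its continuous endpoints for baseline.

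**Conclusion.** The point holds as a matter of precision and clarity. The example conflicts with the entry criterion and should be replaced. The response threshold depends on baseline IGA while the test ignores it, so a chance gap in the 3/4 mix adds noise to the arm difference. A gap of at least 20 points has probability 26% to 37% for true IGA 4 shares of 20% to 50%.

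The consequence is modest: 1 to 6 points on the arm difference for a 20-point gap under the rates assumed here, against a standard error of up to about 15 points. These sizes rest on response rates by baseline score that the documents do not supply, and on criterion 3 being read as IGA 3 or 4. There is no systematic bias and no overall type I inflation. The endpoint is secondary and its p-value descriptive. The change is worth making because it costs very little, not because the result would otherwise be invalid.

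**What to change.** 1. In SAP 6.2, compare the arms on this endpoint with a Cochran-Mantel-Haenszel test and a Mantel-Haenszel risk difference with 95% interval, stratified by baseline static IGA (3, 4). Use an exact version if the table is sparse. State beforehand how a subject enrolled in error at another score is handled, for instance by pooling with the nearer stratum.
2. In Protocol 8.5.2 and SAP 6.2, replace the example with the two cases that can occur: from 4 to 2 or less, and from 3 to 1 or less. Put the minimum wording into Protocol 1.0 and 3.2 and SAP 3.6.
3. Name baseline static IGA by arm in SAP 6.10.2, as Protocol 8.3 requires, and add a baseline-to-Week-12 static IGA shift table by arm. Baseline PASI and %BSA need no change.
4. Add one sentence saying that, among eligible subjects, IGA 0/1 implies a 2-step reduction.

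The cost is minor edits to both documents, one stratified analysis in place of a simple one, and one table from data already collected. The drawbacks are small strata and a gain that may be close to nil if response hardly differs by baseline score. The changes should be fixed before unblinding.

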6.3 Exploratory Efficacy Endpoints Analyses

The following exploratory efficacy endpoints will be summarized and compared between the LYC-30937-EC treatment arm and placebo:

- The proportion of subjects who achieve a $\geq 50\%$ reduction from baseline in PASI at Week 12 will be calculated by taking the number of subjects who achieve a percent change from baseline at Week 12 in PASI score $\geq 50\%$ divided by the total number of subjects in each treatment group. The proportion of subjects in each treatment group will be compared using chi-square test. The difference in proportion of subjects who achieve a $\geq 50\%$ reduction from baseline in PASI score at Week 12 (LYC-30937-EC versus placebo) will also be estimated along with the 95% confidence interval. If the confidence interval does not contain 0 the null hypothesis will be rejected and the proportion of subjects who achieve a $\geq 50\%$ reduction from baseline in PASI score at Week 12 will be considered different due to treatment arm.
- The proportion of subjects who achieve a $\geq 25\%$ reduction from baseline in PASI at Week 12 will be calculated by taking the number of subjects who achieve a percent change from baseline at Week 12 in PASI score $\geq 25\%$ divided by the total number of subjects in each treatment group. The proportion of subjects in each treatment group will be compared using chi-square test. The difference in

proportion of subjects who achieve a $\geq 25\%$ reduction from baseline in PASI score at Week 12 (LYC-30937-EC versus placebo) will also be estimated along with the 95% confidence interval. If the confidence interval does not contain 0 the null hypothesis will be rejected and the proportion of subjects who achieve a $\geq 25\%$ reduction from baseline in PASI score at Week 12 will be considered different due to treatment arm.

- Proportion of subjects achieving both a $\geq 75\%$ reduction from baseline in PASI and static IGA score of 0 (cleared) or 1 (minimal) at Week 12 in each treatment group will be compared using chi-square test. The difference in proportion of subjects who achieve both a $\geq 75\%$ reduction from baseline in PASI score and a static IGA score of 0 or 1 at Week 12 (LYC-30937-EC versus placebo) will also be estimated along with the 95% confidence interval. If the confidence interval does not contain 0 the null hypothesis will be rejected and the proportion of subjects who achieve both a $\geq 75\%$ reduction from baseline in PASI score at Week 12 and a static IGA score of 0 or 1 will be considered different due to treatment arm.

6.4 Safety Analyses

Safety is assessed through the analysis of AEs, clinical laboratory assessments, vital signs, ECGs, and physical examinations. All Safety analyses will be completed on the Safety Population and will include descriptive statistics only.

Unless otherwise specified, safety analyses that include summaries of number and percent (e.g., AEs) will be displayed by treatment groups and overall.

All safety parameters will be listed by subject, treatment group and time point. Adverse events reported by screen failures will be included in a separate listing.

6.5 Adverse Events

Adverse event tables will only include summaries of treatment-emergent adverse events (TEAE). TEAEs are defined as AEs which first occur, or worsen, after the first dose of study drug and within 14 days after the permanent discontinuation of the study drug (i.e., first dose date \leq AE start date \leq last dose date + 14 days).

Severity of AEs will be graded according to National Cancer Institute Common Terminology Criteria for Adverse Events (NCI CTCAE) v4.03.

All TEAEs will be summarized by system organ class (SOC) and preferred term and by descending frequency of preferred terms, by maximum severity (maximum NCI CTCAE grade), and by strongest relationship to study treatment. This will be done by treatment group and overall.

For subjects not randomized, only SAEs and AEs leading to screen failure will be collected on the CRFs from the time the subject has signed informed consent. If reported, these AEs/SAEs will be listed by subject.

Below are the rules to follow for AE summaries:

- For the summary of AEs by severity, if a subject has multiple events occurring in the same body system or same preferred term, then the event with the highest NCI CTCAE grade will be counted. AEs for which the severity is missing are counted only in the overall column.
- A related AE is defined as an AE with an assigned causality of “related,” “suspected,” or if causality is missing.
- Refer to Appendix 3 for details of imputing partial dates for AE.

AEs will be coded using MedDRA version 19.0.

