4.0 STUDY DESIGN

4.1 Design Overview

This is a phase 2a multi-center, randomized, double-blind, placebo-controlled, parallel-group study designed to evaluate the efficacy, safety and tolerability of LYC-30937-EC treatment in subjects with chronic plaque-type psoriasis.

After signing an informed consent, all eligible subjects will be followed for approximately 16 weeks, which includes up to 2 weeks between screening and Study Day 1 (first dose of treatment), 12 weeks for treatment, and 2 weeks for follow-up.

There are 3 distinct phases of this study outlined below:

Screening: The screening visit will take place up to 2 weeks prior to randomization and subject’s first dose of LYC-30937-EC (or matching placebo). Subjects who meet all eligibility requirements will return for the next phase of the study.

Treatment Period: Subjects meeting all entry criteria will be randomized in a 2:1 ratio to active treatment (LYC-30937-EC 25 mg q.d.) or matching placebo. Subjects will receive their first dose of study drug at the investigational site after randomization has occurred. Subjects will return to the investigational site at Weeks 2, 4, 8, and 12 for efficacy assessments, safety monitoring, and study drug receipt (at Weeks 2, 4, 8).

LYC-30937

Clinical Protocol LYC-30937-2003

Issue Date: 30 August 2016

Follow-Up: There will be 1 follow-up visit performed at Week 14 for final safety monitoring purposes.

After completion of all follow-up visits, the study database will be locked to allow for the analysis of data collected up through Week 14.

The subjects, site personnel following the subject, and the sponsor will remain blinded to treatment until after the database lock.

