5.2 Treatment Regimen

The treatment (LYC-30937-EC or placebo) will be administered orally q.d. from Study Day 1 through the end of the double-blind treatment phase (Visit 6/Week 12) for a total of 84 days of treatment. The capsules must be administered in the morning upon awakening after fasting

LYC-30937

Clinical Protocol LYC-30937-2003

Issue Date: 30 August 2016

overnight. Subject should not eat for approximately 1 hour (or more) after taking study drug.

The exception to this is the Visit 2/randomization visit when the first dose of study drug is administered in the clinic. Subjects may have eaten their morning meal prior to coming for this visit. They should note the time they ate their last meal prior to this clinic visit and study drug should not be administered until at least 2 hours after that meal.

- LYC-30937-EC 25 mg q.d.: one 25-mg capsule of LYC-30937-EC, administer upon awaking in the morning after fasting overnight and do not eat within the next approximately 1 hour after dosing
- placebo q.d.: one matching placebo capsule, administer upon awaking in the morning after fasting overnight and do not eat within the next approximately 1 hour after dosing

At the clinic, the study drug supplies must be handled and stored safely and properly, and kept in a secured location to which only the investigator and authorized staff have access.

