6.0 STUDY PROCEDURES

6.1 Visit Timing

The schedule of study procedures is below (Table 1); however, a subject may be seen at any time for safety reasons. Routine clinic visits outlined in the protocol should occur whenever possible at the same time of day throughout the study to decrease variation in assessments and procedures. Prior to each clinic visit, subject activities should remain consistent with their normal routine (eg, meals, medications, caffeine ingestion). Subjects should take prescribed and over-the-counter medications at the same time of the day throughout the study.

- The day the subject receives the first dose of study drug is defined as Study Day 1. The timing of all study visits are based on Study Day 1.
- Study visit timing and windows are as follows:
 - Screening (Visit 1) – approximately Study Day -14 to Day -1
 - Randomization/treatment (Visit 2) – Study Day 1
 - Visit 3 (Week 2 – Study Day 15) – window \pm 2 days
 - Visit 4 (Week 4 – Study Day 29) – window \pm 2 days
 - Visit 5 (Week 8 – Study Day 57) – window \pm 3 days
 - Visit 6 (Week 12 – Study Day 85) – window \pm 3 days
 - Follow-up (Visit 7) (Week 14 - Study Day 99) – window \pm 3 days

Unplanned visits may occur at any time for reasons of safety. These visits and associated procedures must be documented on the CRF.

LYC-30937
Clinical Protocol LYC-30937-2003
 Issue Date: 30 August 2016

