For all SAEs, the investigator is obligated to pursue and provide information to Lycera or designee in accordance with the timeframes for reporting specified above. In addition, an investigator may be requested by Lycera to obtain specific additional follow-up information in an expedited fashion. In general, the SAE form will include a description/narrative of the event in sufficient detail to allow for a complete medical assessment of the case and independent determination of possible causality. Information on other possible causes of the event, such as concomitant medications and illnesses must be provided. In the case of a subject death, a summary of available autopsy findings must be submitted as soon as possible to Lycera or its designated representative. Expedited safety reports on all unexpected SAEs that are at least possibly related to study procedures will be provided to the FDA.

Subjects with unresolved previously reported SAEs, or new SAEs identified on the last scheduled visit, should be followed by the investigator until the events are satisfactorily resolved. Resolution means the subject has returned to the baseline state of health, the investigator does not expect any further improvement or worsening of the AE, or upon agreement with Lycera or designee.

LYC-30937

Clinical Protocol LYC-30937-2003

Issue Date: 30 August 2016

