8.6 Safety Analysis

Adverse event collection begins after the subject signs the informed consent document and continues until Week 14. For all randomized subjects, AEs should be recorded on CRFs from the time the subject has signed informed consent through Week 14. For subjects not randomized, only SAEs and AEs leading to screen failure will be collected from the time the subject has signed informed consent through screen failure. Treatment-emergent AEs are defined as AEs that start after study drug administration (LYC-30937-EC or placebo) and include worsening of conditions that existed prior to study drug administration. Adverse events

LYC-30937

Clinical Protocol LYC-30937-2003

Issue Date: 30 August 2016

that occur in subjects who screen fail will only be listed if they were the reason the subject was a screen failure.

Adverse events and SAEs will be summarized by system organ class, by severity, and by relationship; this will be done by treatment group and overall. Serious adverse events resulting in death will be listed and summarized separately.

Other safety data, such as vital signs and clinical laboratory data will be summarized by study visit and treatment group. Where appropriate, change from baseline in safety data will also be summarized for each study visit, for end of treatment visit, and for “worse value” by treatment group.

LYC-30937

Clinical Protocol LYC-30937-2003

Issue Date: 30 August 2016

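### SAP 6.5 adds an undeclared end limit (last dose + 14 days) to the protocol's TEAE definition, which can cut the AE tables off before the Week 14 safety visit

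*SAP*

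**What the plan says.** Protocol 8.6 gives the definition: "Treatment-emergent AEs are defined as AEs that start after study drug administration (LYC-30937-EC or placebo"), and it also counts worsening of earlier conditions. It names no latest onset date. The only end point in that section concerns collection: "Adverse event collection begins after the subject signs the informed consent document and continues until Week 14". Protocol 4.1 describes the Week 14 visit as the final safety check, after which "the study database will be locked to allow for the analysis of data collected up through Week 14".

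SAP 6.5 keeps the start of the period but closes it. The AE must first occur or worsen "after the first dose of study drug and within 14 days after the permanent discontinuation of the study drug", written as a formula in which the AE start date is no later than the last dose date plus 14 days. The same section confines the AE tables to TEAEs.

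SAP 7 lists the changes from the protocol. It has an item on AE reporting, which drops the summaries of serious AEs (SAEs) and the separate listing and summary of deaths. It does not mention the TEAE definition.

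**The concern.** The SAP narrows a definition that the protocol already states, and a reader who relies on section 7 would not know it. The limit also follows a different clock from the visit it appears meant to reach. Visit 7 is scheduled from Study Day 1 with a window of 3 days either side, while the limit follows each subject's own last dose. A subject who keeps fully to the protocol can therefore attend the final safety visit after the TEAE period has closed.

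The rule tests onset date, not the date of detection. An AE that began before the limit and is first reported at Week 14 is still tabulated. What drops out is an AE whose onset is dated after the limit. One example is a confirmed, clinically significant laboratory abnormality first seen at Week 14, which Protocol 6.4.4 requires to be captured as an AE, if its onset is dated to that visit. Such an event would be missing from the incidence, severity and relationship tables by arm. Because section 7 also drops the SAE and death summaries, no other AE table would show a late-onset SAE.

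With 20 and 10 subjects planned per arm, one omitted event lowers an arm's incidence by 1/20 = 5 or 1/10 = 10 percentage points, if that subject has no other event in the category.

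**Working it through.** **Inputs**
- Visit 6: Day 85, window ± 3, so Days 82 to 88 (Protocol 6.1, Table 1).
- Visit 7: Day 99, window ± 3, so Days 96 to 102 (same places).
- Limit: last dose day L + 14 (SAP 6.5).
- Last dose: Protocol 5.2 has dosing "from Study Day 1 through the end of the double-blind treatment phase (Visit 6/Week 12) for a total of 84 days of treatment". Eighty-four daily doses from Day 1 end on Day 84. Dosing through Visit 6, with home dosing on clinic days (Protocol 5.5.2), ends on Day 85. The documents do not settle which, so both are carried.

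**The plan's own calendar.** Visit day = 1 + 7 × week. Week 12 gives 1 + 84 = 85 and Week 14 gives 1 + 98 = 99. Both match Protocol 6.1.

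**Gap for a given last dose.** Gap = max(0, Visit 7 day − (L + 14)).

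| Last dose | Limit | Visit on Day 96 | Day 99 | Day 102 |
|---|---|---|---|---|
| Day 81 | Day 95 | 1 | 4 | 7 |
| Day 82 | Day 96 | 0 | 3 | 6 |
| Day 84 | Day 98 | 0 | 1 | 4 |
| Day 85 | Day 99 | 0 | 0 | 3 |
| Day 88 | Day 102 | 0 | 0 | 0 |

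With the last dose on Day 84, 4 of the 7 allowed visit days (99 to 102) lie beyond the limit. With Day 85, 3 of 7 do (100 to 102).

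**All allowed pairs of visit days.** Write Visit 6 = 82 + a and Visit 7 = 96 + b, with a and b each from 0 to 6: 7 × 7 = 49 pairs.
- Last dose on the Visit 6 day: Visit 7 − limit = (96 + b) − (82 + a + 14) = b − a. This is positive when b > a: 6 + 5 + 4 + 3 + 2 + 1 = 21 of 49 pairs, with gaps of 1 to 6 days.
- Last dose the day before Visit 6: the difference is b − a + 1. This is positive when b ≥ a: 7 + 6 + 5 + 4 + 3 + 2 + 1 = 28 of 49 pairs, with gaps of 1 to 7 days.

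These are counts of calendar pairs. They are not probabilities, shares of subjects or shares of events.

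**Early stoppers.** A last dose on Day 56, for example, puts the limit on Day 70, which is 99 − 70 = 29 days before the nominal final visit. This matters only if such subjects are followed for more than 14 days after their last dose. The documents do not make that clear: Protocol 4.5 asks for Week 12 procedures where possible, and Protocol 6.4.6 speaks in places of stopping drug and in others of withdrawal from the study.

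**The case against.** The 14 days has an evident source. SAP 2.1 places the follow-up visit two weeks after the end of treatment, and Protocol 4.1 plans two weeks of follow-up. The limit therefore looks like an attempt to match the end of AE collection that misses by visit tolerance, and Protocol 8.4 leaves further analysis detail to the SAP. A fixed post-dose window is an ordinary choice. The nominal gap is 0 or 1 day.

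The pair counts also look larger than the effect. Averaged over the 49 pairs the gap is 56/49 = 1.1 days or 84/49 = 1.7 days, and gaps of at most 3 days make up 15 of the 21 and 18 of the 28. Week 14 laboratory values remain summarized by arm (SAP 6.6), as do vital signs (SAP 6.7), and excluded AEs stay in by-subject listings (SAP 6.4). The protocol's mention of "new SAEs identified on the last scheduled visit" (section 7.5) concerns identification and follow-up, not onset, so it does not show that an SAE would be lost.

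Most of this stands as a statement of size. It does not remove the point. Knowing where the 14 days came from does not align two clocks that start from different days. Narrowing a definition the protocol already gives is a change, not added detail, and section 7 exists to record such changes. Laboratory and vital sign summaries do not replace AE incidence, severity and relationship by arm.

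**Conclusion.** The concern holds. The protocol sets no upper limit on TEAE onset, SAP 6.5 adds one, section 7 does not declare it, and it can close before the final safety visit even in a fully compliant subject. For completers the gap is 0 or 1 day at nominal visit days and at most 6 or 7 days within the windows, depending on whether the last dose is taken on the Visit 6 day or the day before.

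The consequence is limited to which AEs are tabulated by arm. Whether any event is lost depends on its onset being dated after the limit; the documents give no rule for dating the onset of a finding made at a visit, so the laboratory example is an assumption. The early-stopper case is conditional and adds no firm figure. This should be fixed, though it does not threaten the trial's main conclusions.

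**What to change.** In SAP 6.5, define a TEAE as an AE that starts or worsens after the first dose and up to the last study visit (Week 14). This keeps the protocol's open definition and uses its end of collection as the end of the period. If an on-drug window is wanted, split the tables at last dose + 14 days.

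If the sponsor prefers to keep a limit, list it in SAP 7 as a departure from Protocol 8.6 with the reason, and tabulate later-onset AEs separately by arm. Declaring it alone would leave those events out of every AE table. A fixed limit that covers every allowed visit date would need 102 − 82 = 20 days after the last dose if that dose is on the Visit 6 day, or 102 − 81 = 21 days if it is the day before. The passages that give the planned last dose should be reconciled in either case.

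The cost is one line in section 6.5 and, if a limit is kept, one line in section 7 plus the added tabulation. No extra data are needed. The small downside is that a few off-drug events enter the tables, which the optional split would show.
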